7.3.5. Subject's Assessment of Response to rFIXFc Injections for Bleeding

Each subject or subject's caregiver will provide an assessment of response to each administration of rFIXFc for each bleeding episode using the 4-point scale of excellent, good, moderate, and none (see Appendix A for further details; 'none' means that there was no improvement, not that the subject did not provide a response). Response categories of excellent and good will be presented combined as well as individually. The number and percentage of injections in each response category will be tabulated based on all injections. Two summaries will be provided. In the first summary, percentages will be based on the total number of injections administered for bleeding episodes for which a response was provided. In the second summary, percentages will be based on the total number of bleeding episodes whether or not a response was provided. As a

supplemental analysis, similar summaries will be provided based on just the first injection administered after each bleeding episode using both approaches to determine the percentages.

The subject's assessment of response will be summarized for the FAS as follows:

- For subjects from study 998HB102, it will be summarized by treatment regimen in study 9HB01EXT.
- For subjects from study 9HB02PED, it will be summarized by age cohort (<6 years old and 6 to <12 years old) from study 9HB02PED and treatment regimen in study 9HB01EXT.

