7.1.4.2. Procedure to Treat the Bleeding Episode

The dose of rFIXFc to treat the bleeding episode will be based on the subject's clinical condition, known PK information from the previous study or FIX trough and/or peak (recovery) measurements in this study, type and severity of the bleeding event (see [Appendix A](#) for guidance on dosing), and input from the Sponsor, if necessary.

Subjects and subjects' caregivers should be instructed to treat at the first sign of a bleeding episode and with a single dose of rFIXFc. Most bleeding episodes should resolve with a single dose of rFIXFc. If a subject has one spontaneous bleed and the Investigator is concerned the trough level is too low, the Investigator should contact the Sponsor to discuss next steps for this subject.

- **If the bleeding episode stops with a single IV dose of rFIXFc**, the subject should return to his previous dosing regimen and will be treated with his next dose of rFIXFc, as previously scheduled, even if this results in consecutive daily doses.
- **If the bleeding episode does not stop within 48 hours with the single IV dose of rFIXFc**, the subject or the subject's caregiver should consult with the Investigator for an optimal rFIXFc dose and dosing interval. Because of the long lasting effect of

CONFIDENTIAL

The information contained herein may not be used, disclosed, or published without the written consent of
Biogen Idec MA Inc.

rFIXFc, it is recommended that the subject takes the first follow-up dose no less than 48 hours after the initial dose. However, if the subject experiences persistent pain or other signs of ongoing bleeding, the first follow-up dose may be administered before 48 hours. Administration of the second dose of rFIXFc as a follow-up treatment will be determined by the Investigator, based on the subject's clinical condition. Please refer to [Appendix A](#) for rFIXFc dosing guidance. Once the bleeding event stops, the subject will return to his previous dosing regimen and will be treated with his next dose of rFIXFc as previously scheduled, even if this results in consecutive daily doses.

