- **If the bleeding event does not stop with 2 doses (initial and follow-up treatments) of rFIXFc**, the subject or the subject's caregiver should contact the Investigator for advice. Following consultation with the Investigator, a third dose of rFIXFc will be administered 48 hours after the administration of the second dose of rFIXFc. The third dose (second follow-up dose) may be at the same dose level as the second dose or a dose determined by the Investigator based on the subject's clinical condition. Please refer to [Appendix A](#) for rFIXFc dosing guidance. Once the bleeding event resolves, the subject will return to his previous dosing regimen and will be treated with his next dose of rFIXFc as previously scheduled, even if this results in consecutive daily doses.
- **If the bleeding event still has not stopped after 3 doses (initial and 2 follow-up doses) of rFIXFc**, the Investigator should contact the Sponsor Medical Monitor to discuss the next steps for treatment of the subject.

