16.4.3.2. Other Efficacy Endpoints

The response to treatment for bleeding will be summarized by the number and percentage of bleeding episodes for each response (excellent, good, moderate, none). These data will be summarized overall during each study based on the FAS.

CONFIDENTIAL

The information contained herein may not be used, disclosed, or published without the written consent of Biogen Idec MA Inc.

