7.4. Additional Assessments

7.4.1. Number of Injections and Dose of rFIXFc to Resolve a Bleeding Episode

The number of injections, average dose per injection (IU/kg), and total dose (IU/kg) required to resolve a bleeding episode will be determined on both a per-bleeding episode and per-subject basis. See Section 7.1.1 for details on the definition of a bleeding episode. A bleeding episode is considered resolved when treatment for the bleeding is no longer needed.

Per bleeding episode: The total number of injections will include the initial injection for a spontaneous bleed (SB), a traumatic bleed (TB), or a bleed of unknown type plus all injections identified as follow-up (FU) treatment for that bleed. For each bleed, the average dose per injection will be calculated as the average of all doses (IU/kg) administered among the SB/TB/Unknown and FU injections administered to treat that bleed; the total dose will be the sum of these doses. The number of injections required for the resolution of a bleeding episode will be summarized across all bleeding episodes in study 9HB01EXT both categorically (1, 2, 3, >3; 1, >1; and ≤ 2 , >2) and with descriptive statistics. The average dose per injection and total dose required for resolution of a bleeding episode will be summarized using descriptive statistics.

Per subject: The number of injections, average dose per injection, and total dose required to resolve each bleeding episode, as determined for the per-bleeding episode summaries, will be averaged across all bleeding episodes in study 9HB01EXT for each subject. The average number of injections required for resolution of a bleeding episode will be summarized both categorically (1 to <2, 2 to <3, and ≥ 3) and with descriptive statistics. The averages for the per subject average dose per injection and total dose required for resolution of a bleeding episode will be summarized using descriptive statistics.

Bleeding episodes that were treated with both study and non-study medication will be included in the determination of the number of injections required to resolve the bleeding episode but not in either the average dose per injection or total dose required.

For the above analysis, data from the FAS will be summarized as follows:

- For subjects from study 998HB102, it will be summarized by treatment regimen in study 9HB01EXT.

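### SAP 7.3.5: the second all-injections summary of bleed response divides injections by bleeding episodes, so its percentages are inflated by injections per bleed and can pass 100%

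*SAP*

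**What the plan says.** The subject's or caregiver's response to treatment of bleeds is a listed secondary endpoint (Protocol 6.2.2, SAP 2.2.2). SAP 7.3.5 sets it out in four steps.

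- **Rating unit.** The subject or caregiver gives an "assessment of response to each administration of rFIXFc for each bleeding episode", so a bleed treated more than once can carry more than one rating.
- **Numerator.** "The number and percentage of injections in each response category will be tabulated based on all injections".
- **First denominator.** "In the first summary, percentages will be based on the total number of injections administered for bleeding episodes for which a response was provided". Read as rated injections, this matches the numerator.
- **Second denominator.** "In the second summary, percentages will be based on the total number of bleeding episodes whether or not a response was provided".

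A supplemental analysis repeats both summaries for the first injection of each bleed, which makes four displays in all. Protocol 16.4.3.2 uses bleeds as its unit: "The response to treatment for bleeding will be summarized by the number and percentage of bleeding episodes for each response".

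**The concern.** The second summary differs from the first by keeping unrated items in the denominator, so its use is to show how far missing ratings could matter. In the all-injections version it also changes the unit from injections to bleeds, and the result is not a percentage of anything. Repeat injections push it up and missing ratings pull it down. A reader comparing the two summaries cannot tell which effect is being seen.

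The risk is greater when the output looks plausible. A figure above 100% would be queried. A set of categories adding to 100% or less would not, even with the excellent/good line overstated. The error favours the product, and the same table is rerun in the impact assessment (SAP 9.2, Table 5). There, reverting diary changes and dropping unsupported records can alter the number of injections per bleed, so the two runs could agree or differ for reasons unrelated to response.

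**Working it through.** The plan states no figure for this point, so there is none to reproduce. The check is ratio arithmetic on the stated rule.

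**Can a bleed have more than one injection?** Yes. SAP 7.4.1 counts the initial injection "plus all injections identified as follow-up (FU) treatment for that bleed". Protocol 7.1.4.2 allows for follow-up treatment and says "a third dose of rFIXFc will be administered 48 hours after the administration of the second dose of rFIXFc" if two doses do not stop the bleed. SAP 7.1.1 keeps injections up to 72 hours apart within one bleed, so doses at about 48 hours stay in the same episode.

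**Symbols.** None of the three values is in the documents, so all are assumptions.

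- m = rFIXFc injections for bleeds ÷ bleeds counted. Range 1.05 to 1.5. It may be near 1, because Protocol 7.1.4.2 says "Most bleeding episodes should resolve with a single dose of rFIXFc".
- q = share of those injections rated. Range 0.8 to 1.0.
- p = share of rated injections that are excellent or good. Taken as 0.9, then varied to 0.7.

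**Formulas for the excellent/good line.** With B bleeds there are mB injections, of which mBq are rated and mBqp are excellent or good.

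- First summary: mBqp / mBq = p
- Second summary, matched units: mBqp / mB = pq
- Second summary, as written: mBqp / B = pqm
- Inflation factor: pqm / pq = m
- Sum of the four categories as written: qm

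**Results at p = 0.9** (first summary 90% throughout):

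| q | Matched units | As written, m = 1.05 | m = 1.12 | m = 1.25 | m = 1.5 |
|---|---|---|---|---|---|
| 0.8 | 72% | 75.6% | 80.6% | 90.0% | 108.0% |
| 0.9 | 81% | 85.1% | 90.7% | 101.3% | 121.5% |
| 1.0 | 90% | 94.5% | 100.8% | 112.5% | 135.0% |

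The excess is pq(m − 1). At q = 0.8 it is 3.6, 8.6, 18.0 and 36.0 points across the four values of m.

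**Lower p.** At m = 1.5 and q = 0.8, the line as written is 96.0% for p = 0.8 (matched 64%) and 84.0% for p = 0.7 (matched 56%). It stays below 100% but is still 1.5 times too high.

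**Thresholds.**

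- The excellent/good line passes 100% when m > 1/(pq). For p = 0.9 that is 1.39, 1.23 and 1.11 at q = 0.8, 0.9 and 1.0.
- The four categories together pass 100%, and the second summary exceeds the first, when m > 1/q: 1.25, 1.11 and 1.00.

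**The case that hides the error.** At m = 1.25 and q = 0.8, qm = 1.00. The categories add to exactly 100% and the line reads 90%, the same as the first summary.

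**What m = 1.25 could look like.** Suppose that of 100 bleeds, 80 take one injection, 15 take two and 5 take three: 80 + 30 + 15 = 125 injections, and 125/100 = 1.25.

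**First-injection tables.** There is at most one injection per bleed, so this inflation does not arise.

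**The case against.** The best case against is that the sentence has lost a few words. It runs parallel to the first-summary sentence, follows one that bases the tabulation on all injections, and sits under a default in SAP 5.2.2 that points to a single unit per percentage. The table shells mentioned in SAP 5.2.1 are not among the documents and may already carry the right denominator. A slip is quite possible. But the SAP 5.2.2 default yields where a section specifies otherwise, as this one does, and a programmer following the text would produce the wrong table.

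A second reading takes the bleed as the rated unit, as in Protocol 16.4.3.2, so that both parts of the fraction count bleeds. That conflicts with the stated percentage of injections, and the SAP gives no rule for reducing several ratings to one per bleed.

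Three points stand as limits:

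- SAP 7.1.1 also counts bleeds treated only with non-study FIX. These enter the denominator with no rFIXFc injection to rate, so m must be read as rFIXFc injections over all counted bleeds, and the inflation is somewhat smaller if such bleeds occur.
- Any injection more than 72 hours after the preceding one starts a new bleed, which also lowers m.
- If the table prints both injection and bleed counts, a careful reader could recompute the matched figure, helped by the injections-per-bleed table of SAP 7.4.1.

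**Conclusion.** The concern holds. As worded, one of the four displays for this secondary endpoint mixes units, and each of its percentages is m times the matched value. Over the assumed ranges at p = 0.9, the excess in the excellent/good line runs from 3.6 points (m = 1.05, q = 0.8) to 45.0 points (m = 1.5, q = 1.0). If most bleeds do need one dose, the lower end is the likelier. Values above 100% are possible, not certain.

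The factor scales all four categories alike, and SAP 7.1.2 confirms that no tests are done on efficacy endpoints, so no decision rule changes. What is lost is the one use of the display, which is to show the effect of missing ratings. It should be fixed before the tables are run.

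**What to change.** In SAP 7.3.5, for the all-injections table, make the second denominator every rFIXFc injection given to treat a bleeding episode, rated or not. Keep bleeding episodes as the denominator only for the first-injection table, where at most one injection is counted per bleed and the unit agrees with Protocol 16.4.3.2. State there whether bleeds treated only with non-study FIX are counted. Print the injection and bleed counts in both tables.

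Carry the change to the impact-assessment rerun in SAP 9.2, Table 5, which lists the same program, T-SUBJ-ASSESS-RESP-BLD.SAS. The main cost is one SAP sentence and one denominator in that program, with a short note for the non-study FIX bleeds. No new data are needed.

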7.4. Additional Assessments

7.4.1. Number of Injections and Dose of rFIXFc to Resolve a Bleeding Episode

The number of injections, average dose per injection (IU/kg), and total dose (IU/kg) required to resolve a bleeding episode will be determined on both a per-bleeding episode and per-subject basis. See Section 7.1.1 for details on the definition of a bleeding episode. A bleeding episode is considered resolved when treatment for the bleeding is no longer needed.

Per bleeding episode: The total number of injections will include the initial injection for a spontaneous bleed (SB), a traumatic bleed (TB), or a bleed of unknown type plus all injections identified as follow-up (FU) treatment for that bleed. For each bleed, the average dose per injection will be calculated as the average of all doses (IU/kg) administered among the SB/TB/Unknown and FU injections administered to treat that bleed; the total dose will be the sum of these doses. The number of injections required for the resolution of a bleeding episode will be summarized across all bleeding episodes in study 9HB01EXT both categorically (1, 2, 3, >3; 1, >1; and ≤ 2 , >2) and with descriptive statistics. The average dose per injection and total dose required for resolution of a bleeding episode will be summarized using descriptive statistics.

Per subject: The number of injections, average dose per injection, and total dose required to resolve each bleeding episode, as determined for the per-bleeding episode summaries, will be averaged across all bleeding episodes in study 9HB01EXT for each subject. The average number of injections required for resolution of a bleeding episode will be summarized both categorically (1 to <2, 2 to <3, and ≥ 3) and with descriptive statistics. The averages for the per subject average dose per injection and total dose required for resolution of a bleeding episode will be summarized using descriptive statistics.

Bleeding episodes that were treated with both study and non-study medication will be included in the determination of the number of injections required to resolve the bleeding episode but not in either the average dose per injection or total dose required.

For the above analysis, data from the FAS will be summarized as follows:

- For subjects from study 998HB102, it will be summarized by treatment regimen in study 9HB01EXT.
- For subjects from study 9HB02PED, it will be summarized by age cohort (<6 years old and 6 to <12 years old) from study 9HB02PED and treatment regimen in study 9HB01EXT.

7.4.2. Time from Last Injection of rFIXFc to a Bleeding Episode

The time (in days) between a spontaneous bleeding episode and the most recent previous prophylaxis injection of rFIXFc, will be calculated and summarized by treatment regimen in study 9HB01EXT using descriptive statistics. Time will be determined in minutes and then converted to days as total minutes divided by 1440. Of note, the reference time for the bleeding episode is the onset of the bleed and not the time treatment for the bleed was first administered. The definition of a new bleeding episode can be found in Section 7.1.1.

The time from the last prophylactic injection to a new spontaneous bleeding episode will be determined on both a per-bleeding episode and per-subject basis. Each evaluable spontaneous bleeding episode will be included as a separate observation in the summary statistics for the per-bleeding episode evaluation. Evaluable bleeding episodes are those for which both a date and time are available for both the onset of the bleeding episode and the previous prophylactic injection. For the per-subject evaluations, times will be averaged across all evaluable spontaneous bleeding episodes per subject and descriptive statistics will be provided for this per-subject average time.

Bleeding episodes that were treated with non-study medication will be included in these analyses, regardless of which treatment was administered first, if all other information needed to calculate the endpoint value is available.

7.4.3. Time Between the First and Second Injection to Treat a Bleeding Episode

In order to characterize the resolution of bleeding episodes treated with rFIXFc, the time between the first and second injections to treat a bleeding episode will be determined on both a per-bleeding episode and a per-subject basis.

Per bleeding episode: The time (in hours) between the first and second injections to treat a bleed will be summarized using descriptive statistics across all bleeding episodes, including those with type=Unknown, that required at least 2 injections for resolution.

Per subject: The number of hours between the first and second injections to treat a bleeding episode, as determined for the per-bleeding episode summaries, will be averaged across all evaluable bleeding episodes per subject. Descriptive statistics will be provided for the per-subject average times.

Additionally, the time between the first and second injections to treat a bleed will be summarized per bleeding episode and per subject by treatment regimen in study 9HB01EXT and by type of bleed (spontaneous, traumatic) using descriptive statistics.

Bleeding episodes that were treated with non-study medication will be included in the determination of the time between the first and second injections.

7.4.4. Hemophilia Joint Health Score

Joint assessment will be collected using a modified Hemophilia Joint Health Score (HJHS) for adult subjects and use the HJHS for pediatric subjects.

The Modified HJHS assessment includes the scoring of six joints (left ankle, right ankle, left elbow, right elbow, left knee, right knee) on a scale from 0 to 19 according to the following criteria: swelling, duration, muscle atrophy, crepitus, flexion loss, extension loss, instability,

joint pain, and strength. Gait will be scored on a scale from 0 to 2 based on walking and climbing stairs. The total score will be the sum of scores from all 6 joints plus the gait score (range from 0 to 116, with 0 being normal and 116 being the most severe disease).

The HJHS assessment includes the scoring of six joints (left ankle, right ankle, left elbow, right elbow, left knee, and right knee) on a scale from 0 to 20 according to the following criteria: swelling, duration of swelling, muscle atrophy, crepitus of motion, flexion loss, extension loss, joint pain, and strength. Gait will be scored on a scale from 0 to 4 based on the number of skills that are not within the normal limits. The total score will be the sum of scores from all six joints plus the gait score (range from 0 to 124, with 0 being normal and 124 being the most severe disease), which is auto-populated from eCRF.

In order to make summary statistics interpretable, the total joint score (i.e. sum of scores from all six joints) will be defined and derived as follows:

- the total joint score will be set as missing if any one of the individual item score at any joint is missing;
- the total joint score will be set as missing if scores are evaluated within 2 weeks after a joint or muscle bleeding episode; and
- the total joint score will be re-derived if surgery is performed on a joint. The scores for the joint will be replaced with the scores of the same joint at the last visit prior to the surgery using the last observation carried forward (LOCF) technique. Therefore, the total joint score in the subsequent visit is re-derived using the abovementioned scores. In addition, it should be noted that this includes surgeries in the parent study as well. If the joint surgery indeed is from the parent study, the joint score at the screening visit is used for LOCF because HJHS was performed only at screening visit in the parent study. The total joint score, gait scores, and total score (calculated as the sum of total joint score and gait score that are both present), as well as change from study 9HB01EXT baseline will be summarized by visit for overall treatment regimen for Safety Analysis Set. The study 9HB01EXT baseline is defined above in Section 5.1.2.

Age at the entry of study 9HB01EXT ≥ 4 years old will be applied for subjects from study 9HB02PED for summary tables and will be flagged in the listings well.

Modified HJHS and HJHS scoring details are given in Appendix H.

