10.1.3. Surgery

For subjects who require emergent or elective surgery during the study period, the dose and regimen of rFIXFc shall be that deemed appropriate for the type of surgery to be performed.

All major surgeries must take place in a center that can provide study treatment, trained study personnel, post-operative assessments, and hematological consultations by the Investigator or Sub-Investigator. If the surgery does not occur in such a setting, the subject will be withdrawn from the study.

In addition, subjects who require major surgery may receive rFIXFc if:

1. The surgery occurs within the contracted Institution for the trial and/or a separate agreement has been executed, permitting the use of study drug and Biogen Idec's rights to data generated in the trial at an alternative Institution deemed appropriate by the Investigator.
2. The Investigator and/or appropriate qualified/licensed delegate is available to:
 - a. Administer all the rFIXFc doses required during surgery and during post-operative rehabilitation (if applicable).
 - b. Provide medical oversight and guidance throughout the duration of the pre-operative and the intra-operative periods.

Surgeries, elective or emergent, will be classified as major or minor, as follows:

- Major surgery is defined as any surgical procedure (elective or emergent) that usually, but not always, involves general anesthesia and/or respiratory assistance, in which a major body cavity is penetrated and exposed, or a substantial impairment of physical or physiological functions is produced (e.g., laparotomy, thoracotomy, craniotomy, joint replacement, or limb amputation).
- Minor surgery is defined as any surgical procedure (elective or emergent) that does not involve general anesthesia and/or respiratory assistance (e.g., minor dental extractions, incision, and drainage of abscess, joint or other injections, or simple excisions).

All major surgeries will be reported as SAEs.

CONFIDENTIAL

The information contained herein may not be used, disclosed, or published without the written consent of Biogen Idec MA Inc.

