16.4.2. General Methods of Analysis

All efficacy endpoints are secondary. No imputation will be applied to any missing efficacy data. The periods in which data will be used for efficacy and surgical rehabilitation analyses will be defined in the statistical analysis plan. Data on bleeding and rFIXFc consumption will be based on the efficacy period; surgical evaluations will be based on the surgical/rehabilitation period.

Analysis of efficacy endpoints that are visit-based will include data from all study visits, whether or not they occurred during the efficacy period. However, if a visit is coincidental with a surgical/rehabilitation period for a major surgery, it will be excluded from the analysis.

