5.1.4 Handling of Missing Data

Aside from the following, no imputation of study data will be performed.

- The episodic treatment regimen at the start of study 9HB01EXT will be imputed for the scenario specified in Section 5.3.1.
- The occurrence of a new bleeding episode will be imputed if >72 hours lapse between 2 consecutive injections administered to treat a bleed. Details are provided in Section 7.1.1.

For CHO-KLAT, if a subject has data missing at a particular visit, the total score can still be estimated provided at least 27 of the 35 questions have been answered. If a subject's data cannot be used to calculate an overall score that subject will also be excluded from summaries of individual domains at that visit and will be flagged as excluded from summaries in analysis dataset. Details are provided in Section 7.5.3 and Appendix E.

For HAEMO-QoL and HAEM-A-QoL, and Hemo-Sat, if a subject has data missing at a particular visit for a domain, the total score and subscores will still be estimated provided the questionnaire makes provision for missing domains in the calculation algorithm of overall score. If a subject's data cannot be used to calculate an overall score that subject will also be excluded from summaries of individual domains at that visit and will be flagged as excluded from summaries in the analysis dataset. Details are provided in Sections 7.5.1 and 7.5.2 Appendix C, and F, respectively.

For the analysis of AEs and concomitant medications/procedures, if the stop/start date of an AE/concomitant medication is missing or partial, the corresponding study day will be left blank. However, inferences will be made from the partial and missing dates to classify medications as concomitant, AEs as treatment emergent (or not), and AEs during surgical/rehabilitation period. These inferences are described in Sections 6.4.1 and 8.2, respectively.

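### SAP 7.4.4 overwrites observed HJHS scores after any surgery on a joint, without limiting the rule to major surgery or settling baseline and parent-study cases

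*SAP*

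**What the plan says.** SAP 7.4.4 gives special derivation rules for the sum over six joints and states their purpose: "In order to make summary statistics interpretable, the total joint score" is to follow three rules. Two set the score to missing: when any item is missing, and when the assessment falls within two weeks after a joint or muscle bleed. The third substitutes a value: "the total joint score will be re-derived if surgery is performed on a joint". By last observation carried forward (LOCF), "The scores for the joint will be replaced with the scores of the same joint at the last visit prior to the surgery", and "the total joint score in the subsequent visit is re-derived using the abovementioned scores". Parent-study operations count too: "If the joint surgery indeed is from the parent study, the joint score at the screening visit is used for LOCF". The reason given is that the parent study measured HJHS only at screening.

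SAP 7.4.4 does not define surgery. Protocol 10.1.3 gives as examples of minor surgery "minor dental extractions, incision, and drainage of abscess, joint or other injections, or simple excisions", and names joint replacement as an example of major surgery.

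Baseline is the last non-missing Visit 1 measurement (SAP 5.1.2), set to missing if it falls within a major surgical/rehabilitation period. The footnotes to the protocol's visit schedule ask for a joint score at Visit 1 in every subject. Total joint score, gait, total score and change from baseline are summarized by visit. The output list has one HJHS summary table per parent study and an HJHS listing.

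SAP 5.1.4 says "Aside from the following, no imputation of study data will be performed". The HJHS rule is not among the exceptions that follow.

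**The concern.** The first two rules remove scores judged unreliable. The third replaces a score that was actually observed with an older one. Three features make that a problem.

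- **Trigger.** Read with the protocol's definition, a joint injection is enough to set aside all later assessments of that joint, or at least the next one.
- **Parent-study surgery.** Visit 1 normally comes after such an operation, so change from the 9HB01EXT baseline already leaves out most of the surgical step. Bringing back a pre-surgery screening score corrects nothing in that comparison and can create an error.
- **Unstated scope.** The text does not say whether Visit 1 is replaced as well, or whether the rule covers one later visit or all of them. Two programmers could produce different tables.

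At stake is the by-visit HJHS change. Joints that undergo procedures are plausibly among the more diseased ones (an assumption), where long-term change is of most interest. No planned summary uses the observed scores, so the effect would not show in the tables.

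**Working it through.** **1. Score ranges (SAP Appendix H), reproduced from item maxima.**
- Modified HJHS: 3+1+2+1+3+3+1+1+4 = 19 per joint; 6×19 + 2 (gait) = 116, as stated.
- Pediatric HJHS: 3+1+2+2+3+3+2+4 = 20 per joint; 6×20 + 4 (gait) = 124, as stated.
- Most that one joint can contribute: 19/116 = 16.4%, or 20/124 = 16.1%.

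**2. Is the trigger limited to major surgery?** The SAP writes major where it means only major: SAP 4.4 (surgery subgroup), 5.1.2 (baseline), 7.3.4 (physician's assessment), 7.5 (questionnaires). SAP 5.3.2 and 5.3.3 expressly treat major and minor alike. SAP 7.4.4 has no qualifier. That injections trigger the rule is therefore an inference from the protocol's definition, but it is a natural way to program the text.

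**3. Effect on one joint.** All scores are assumed. HJHS is scheduled at Visits 1, 3, 5 and 7. After the procedure, rule-based change = (score at last pre-procedure visit) − (baseline score). The rule is applied here to all later visits.

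| Case | Scores at V1/V3/V5/V7 | Procedure | Observed change | Change under the rule |
|---|---|---|---|---|
| A | 6/8/9/11 | injection, V1–V3 | +2/+3/+5 | 0/0/0 |
| B | 6/8/9/11 | injection, V3–V5 | +2/+3/+5 | +2/+2/+2 |
| C | 6/10/7/6 | injection, V3–V5 | +4/+1/0 | +4/+4/+4 |
| D | 14/4/4/4 | joint replacement, V1–V3 | −10/−10/−10 | 0/0/0 |

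In A and D the last pre-procedure score is the baseline, so change is 0. In B and C the change stays at what had accrued; in C this overstates the final change (+4 against 0).

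If the rule covers only the next HJHS visit, the later visits revert to observed values: A becomes 0/+3/+5 and B becomes +2/+2/+5.

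**4. Parent-study surgery.** Assumed screening score 14; observed 4/5/6/6 at Visits 1/3/5/7.
- Observed: 5−4, 6−4, 6−4 = +1/+2/+2.
- Rule, baseline also replaced: 14−14 at each visit = 0/0/0.
- Rule, baseline not replaced: 14−4 at each visit = +10/+10/+10, a spurious worsening, because higher scores are worse.

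**5. Cohort mean.** The documents do not give the number of joint procedures. Let a fraction f of subjects have one operated joint before the first post-baseline HJHS, with true mean change d in that joint. Points removed from the cohort mean change = f×d. For f = 0.05–0.30 and d = 1–4 (both assumed): 0.05×1 = 0.05 to 0.30×4 = 1.2 points. If all six joints change equally, the share of the mean joint-score change removed is f/6: 0.05/6 = 0.8% to 0.30/6 = 5.0%.

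**The case against.** The strongest defense is the rule's purpose. After a joint replacement the observed score reflects the procedure, and keeping that gain out of a long-term drug result is reasonable (case D). Restricting the rule to major surgery lets some post-injection change be credited to the regimen, so the choice is partly one of preference. HJHS is an additional assessment in a purely descriptive study, only the operated joint is affected, and a listing is planned. All of this stands. It bears on the size of the problem and supports keeping the rule for major joint surgery. It does not justify the unlimited trigger, the parent-study clause, or the lack of an observed-score summary.

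Stronger readings that the documents do not support:
- **Change is pulled to zero in general.** It is frozen at the pre-procedure value, which may be non-zero or too large (B, C).
- **The joint is frozen for the rest of the study.** SAP 7.4.4 speaks of a single subsequent visit and gives no end point.
- **Parent-study surgery always gives zero change.** Replacement of the Visit 1 baseline is not stated.
- **The rule breaches the protocol's ban on imputing missing efficacy data.** The overwritten scores are not missing, and Protocol 13.5 places HJHS outside the efficacy assessments.
- **It contradicts SAP 5.1.4.** That section concerns missing data and is not exhaustive in practice: SAP 5.3.3 imputes surgery times, and SAP 8.2.4 and 8.2.5 assign missing severity and relationship. What is lacking is a cross-reference.
- **The study has no other long-term joint measure.** Annualized spontaneous joint bleeding is a secondary endpoint.

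**Conclusion.** The point holds in a limited form. As written, SAP 7.4.4 can discard valid scores after any joint procedure and freeze that joint's change at its pre-procedure value. For parent-study surgery it forces zero change or produces a spurious one, depending on a baseline choice the SAP does not state.

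The impact is modest. One joint is at most about 16% of the score range, and the assumed cohort effect is 0.05 to 1.2 points. No hypothesis is tested, so error rates and power are not affected. The conclusion assumes that surgery in SAP 7.4.4 carries the protocol's definition. How often joint procedures occurred cannot be determined from the documents. The parent-study problem does not depend on injections being counted. It does require a Visit 1 baseline after the operation that is not set to missing under SAP 5.1.2.

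**What to change.** In SAP 7.4.4:
- Limit LOCF to major joint surgery, as the protocol defines major surgery, performed after the 9HB01EXT baseline.
- Keep observed scores after minor procedures, including injections, and for surgeries completed before Visit 1. At the least, apply the same replacement to baseline and follow-up.
- State which visits after the surgery are covered.
- Add a by-visit summary of the observed total joint score and its change beside the LOCF version.

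In SAP 5.1.4, add a cross-reference to the rule.

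The cost is SAP wording and one extra table per parent study; no new data are needed. The downside is small: some post-injection change will be attributed to the regimen.
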